9.2 Blinding

The study will use a single-blind design where the study personnel assessing outcomes will be blinded to the study arm to which participants are assigned. To enhance continued blinding of assessors, participants will be asked not to disclose their assigned group during the assessment sessions.

10 Outcomes

10.1 Measures of Physical Performance

The primary efficacy outcome for this study will be the SPPB. The 6MWD, gait speed, and handgrip strength are other important measure of physical function that will be assessed.

10.1.1 SPPB

The SPPB was chosen as the primary outcome because: 1) physical function is an independently important outcome in older persons; 2) the SPPB is a well-accepted, reliable. validated measure of physical function in the older population, (89) and is safe and feasible in clinic, home, and hospital settings, (90) including hospitalized older ADHF patients HF; (28;29;37) 3) the SPPB score is highly predictive of important clinical outcomes, including disability, hospitalization, nursing home admission, and death; (89;91-94) 4) it is sensitive to change in health status(95) and responsive to exercise training;(65;67;96;97) 5) interventions that improve SPPB also improve clinical events, providing independent confirmation of validity; (98;99) 6) the SPPB is a key outcome in LIFE, the largest NIA-funded physical function intervention trial; 7) in our pilot study, the improvement in SPPB explained 90% of the improvement in rehospitalizations, providing a mechanistic link; and 8) the SPPB is standardized, simple, and relatively brief (<10 minutes). The SPPB measures physical function using 3 components: usual gait speed over 4 meters, time to complete 5 chair rises, and standing balance with progressively narrow base of support. Each component is scored on a 0-4 scale and summed for an overall score range of 0-12. Each component of the SPPB is independently associated with important outcomes including mortality.(100:100) Gait speed is associated with survival at increments of 0.1 m/s in community-dwelling adults(101) and is associated with survival in hospitalized older adults with coronary disease.(102)

10.1.2 6MWD

The 6MWD test is a well-established outcome measure in HF. It is valid and reproducible in patients with a wide range of physical function, predicts clinical events, and responds to interventions.(103-106) We showed that it is as predictive of clinical events as exercise oxygen consumption,(107) and improves with exercise training including in older HF patients.(74;108) Although most studies involved outpatients with stable HF, the 6MWD is safe, feasible and

predictive of outcomes in an inpatient population(109) and was feasible, safe, and responsive to the intervention in the REHAB-HF pilot study.(28) The 6MWD will be conducted in an unobstructed hallway, utilizing a standardized script as recommended and as previously reported.(106;107;110) Total distance covered, the number of times and duration of rest, along with symptoms, will be recorded.

10.1.3 Handgrip Strength

Handgrip strength is a simple measure of upper extremity strength that correlates well with lower extremity strength and may serve as a marker of mobility.(111) The measurement is obtained in only a few minutes using a handheld dynamometer. Lower handgrip strength has been associated with increased risk of clinical outcomes including ADL disability (112) and mortality.(100) Cut-off points of < 20 kg in women and < 30 kg in men have been recommended to help identify patients with sarcopenia, a geriatric syndrome characterized by progressive loss of muscle mass and strength (111;113) and has been used as an indicator of frailty.(114)

10.2 Health Status and Quality of Life Measures

10.2.1 Kansas City Cardiomyopathy Questionnaire (KCCQ)

To assess change in health status and health-related QOL, participants will complete the KCCQ, a 23-item self-administered questionnaire that quantifies physical function, symptoms, social function, self-efficacy, and QOL in patients with HF. Scores range from 0-100; higher scores indicate better function. The KCCQ score is an independent predictor of clinical outcomes such as hospitalization and mortality in outpatients with HF,(115;116) and those recently hospitalized for ADHF.(117) It is a reliable and valid measure in HF patients, more sensitive to change than other measures of QOL.(118;119) The KCCQ is also reliable, valid, and responsive in patients with comorbidities.(120) A change in score of as little as 5 points is clinically significant and is associated with changes in clinical status(119) and physical function. A one standard deviation change in 6-minute walk distance correlates with a 5 point change in KCCQ.(121;122) A 5-point change in KCCQ is associated with all-cause mortality, cardiovascular death and hospitalization in patients with HF complicating acute myocardial infarction.(123)

10.2.2 12-Item Short-Form Health Survey (SF-12)

Given the high rates of comorbidities that frequently drive events in this population and which may be impacted by the study intervention, participants will also complete the 12-Item Short-Form Health Survey (SF-12). The SF-12, a quick (2 minute)(124) 12 item health survey is valid and reliable in older adults (125;126) and in HF.(127)

10.2.3 EuroQol (EQ-5D-5L)

This instrument assesses patient-specific health utilities used in cost-effectiveness analyses to capture QOL.(128) It performed well in HF-ACTION(129) and the PROTECT trial of ADHF.(130) It consists of five items that measure difficulty with 1) mobility; 2) self-care; 3) usual activities; 4) pain/discomfort; and 5) anxiety / depression and a self-rating (0-100) "thermometer" of the respondent's overall health. We will use the 5-level version which has improved sensitivity and reduced ceiling effect. It takes approximately 90 sec to complete.(131) When administering the EQ-5D-5L we will discern if participants require assistance with any essential ADLs as identified with responses of 'severe problems' or 'unable to' wash or dress (i.e. the self-care domain).

10.3 Depression, Cognitive Status, and Optimism

10.3.1 Geriatric Depression Scale – 15 (GDS-15)

Depression is common in patients hospitalized with heart failure and is associated with worse clinical outcomes (132;133) and quality of life.(134;135) The Geriatric Depression Scale is a depression screening questionnaire developed specifically for the elderly. The original version consists of 30 'yes/no' questions. A shorter, 15 item version that was subsequently developed (GDS-15) has also been shown to be a valid and reliable screening instrument for depression in an elderly population (136) with sensitivity and specificity similar to the longer 30-item GDS.(137)

10.3.2 Montreal Cognitive Assessment (MoCA)

Cognitive impairment is common in HF patients(138) particularly when recently hospitalized,(139) and is associated with worse clinical outcomes, decreased independence with ADLs, and poorer functional mobility.(139;140) The MoCA, a widely used, sensitive instrument for this purpose, will be used to identify participants with cognitive impairment and assess changes in cognitive status.(141)

10.3.3 Life Orientation Test (LOT-R)

Optimism is broadly defined as the tendency to believe that experiences will lead to good results rather than bad. In other populations, optimism has been associated with decreased readmissions and total mortality. An objective measure of optimism, the revised Life Orientation Test (LOT-R), is easily administered in this population and will be used to determine its stability in patients with heart failure as well as the effect of physical conditioning.

10.4 Accelerometry

An accelerometer (Actigraph GT3X or similar device) will be used to monitor physical activity, movement patterns, and sleep. The device is worn on the wrist, is validated, and is well-accepted (>80% compliance in NHANES). The participant will wear the device from the time of enrollment through final 6-month follow-up.

10.5 Biomarkers and Blood-based Bioenergetic Profiling

To determine if the intervention alters the HF disease course, we selected two well-accepted biomarkers of HF disease severity and prognosis, NT-proBNP(142) and galectin-3;(142) both of which were responsive in HF-ACTION and ASCEND. Tumor necrosis factor alpha, C-reactive protein, and interleukin-6 were selected because we found they were increased in older HF patients and correlated with their SPPB score(143) and are known to predict prognosis. The latter two were also responsive to the physical function intervention in the LIFE study.(144) Twenty mL of venous blood will be drawn at the baseline visit and the 3-month follow-up visit, spun, and frozen at -20°C in 1 mL aliquots, stored locally at -80°C, and shipped in batches to Wake Forest Health on dry ice via overnight transport. Samples will be analyzed later in paired fashion (baseline and follow-up) to minimize inter-batch variability and cost.

Whole blood (16mL at the baseline and 3-month visit) will be drawn for bioenergetics profiling. PBMCs, monocytes, lymphocytes, and platelets will be separated from whole blood and assessed for basal respiration, maximal respiration, ATP-linked respiration, spare respiratory capacity, proton leak, and non-mitochondrial respiration. There may also be a blood draw for up to 2 rehospitalizations, if these occur during the study intervention, at the Wake Forest Clinical Site only.

10.6 Clinical Measures

Clinical events will be collected prospectively from randomization until 6 months after discharge from the index hospitalization, the highest risk period for older ADHF patients, (44) by interviewing participants and family at each visit, phone calls, and medical records review.

10.6.1 Rehospitalizations

All-cause rehospitalization was chosen as the secondary outcome because: 1) it is the most frequent adverse outcome in ADHF; 2) it is associated with impaired physical function, reduced quality of life, increased mortality, and increased cost; and 3) our pilot data and others' suggest that it is responsive to physical function interventions. A rehospitalization will be defined as a hospital stay > 24 hours, including prolonged emergency department visits or observational unit stays, for any cause and categorized according to the recommendations of Horwitz et al.(145) Rehospitalizations will be categorized by the site investigators as primarily due to non-cardiovascular, HF, or other cardiovascular (myocardial infarction, acute coronary syndrome without myocardial infarction, arrhythmia, peripheral vascular) cause, and whether they were related to the study intervention or assessments.

10.6.2 Other Clinical Events

The study will also capture deaths, emergency department visits < 24 hrs, stays at observational units < 24 hrs, unscheduled, urgent medical visits, nursing home placement, myocardial infarction, stroke, serious arrhythmia, syncope, and falls. A fall will be defined as "an unexpected event in which the participants come to rest on the ground, floor, or lower level" as recommended by a recent consensus statement on defining falls as an outcome.(146)

10.7 Frailty

Frailty has been described as a geriatric syndrome characterized by decreased physiologic reserve due to impairment in multiple interrelated systems that results in increased vulnerability to stressors and increased risk for adverse events (147;148). Fried et al developed an operationalized definition of frailty(114)'(149) based on five characteristics: unintentional weight loss; self-reported exhaustion; weakness; slow walking speed; and low physical activity.(150) This now widely adopted frailty phenotype is associated with multiple adverse events, disability and death(114;149) and in HF patients is strongly associated with increased risk of hospitalization.(151) It is dynamic(152) and responds favorably to interventions.(97) For this study, frailty status will be based on modification of the Fried assessment described by McNallan et al(153) for older HF patients using: a) slowness (gait speed by SPPB); b) low physical activity (physical component of SF-12); c) weakness by handgrip strength (dynamometer); d) unexpected weight loss by self report or body mass index <18.5; e) exhaustion based on KCCQ questions 5,6. Participants meeting \geq 3 of these criteria will be classified as frail; those meeting 1 or 2 as pre-frail; and those meeting none as non-frail.

10.8 Timing and Order of Outcome Measures

All baseline assessments are to be collected prior to hospital discharge. Ideally, all measures at all visits will be performed consecutively in 1 period with short-term (~2-5 minute) rest breaks as needed. However, at baseline, extended rest breaks or interruptions to outcomes testing will be allowed to accommodate usual care procedures, visitors, or unusual fatigue.

The order of testing should be kept constant for each participant at each visit. Measures of health status and quality of life should be collected prior to measures of physical performance. Within physical performance, the SPPB should be performed first.

11. Economic Analysis

11.1 Direct Medical Costs

The case report form will be used to collect patient-level information on all-cause medical resource use (hospitalizations, emergency department and urgent care visits, major medical procedures, home and skilled nursing facility care, and outpatient visits) and personnel and capital resources required to provide the REHAB-HF intervention. Medical resource use data will be ascertained by patient self-report and caregiver interviews and supplemented by their medical records. Intervention-related information will be documented by study personnel throughout the study. Direct medical costs will be valued from the societal perspective.(154) Professional services and costs for skilled nursing, home nursing and outpatient visits will be valued using Medicare fee schedules.(155) Costs for emergency department visits and hospitalizations will be estimated using models developed from HF-ACTION based on hospital-level variables (length of stay, reason for admission, major procedures).(156) Cost for the REHAB-HF study intervention will be estimated using our recently-developed TEAM-HF Costing Tool.(157)

11.2 Direct Non-Medical Costs

At 3 months and 6 months, patients will be asked to report information on direct non-medical costs incurred to comply with the REHAB-HF intervention including costs associated with transportation and/or parking and fees for health club memberships, exercise equipment or other services or resources that patients have chosen to purchase to help them adhere to exercise training.

11.3 Indirect (Patient Time) Costs

To estimate time spent on REHAB-HF intervention, we will use information reported within the trial pertaining to adherence to protocol-required rehabilitation sessions and patient-reported information on time spent on home exercise. We will also ask patients to report the total amount of time they spend getting to each rehabilitation session. Indirect costs associated with patient time will be valued using the average hourly wage in the USA.(158)

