7.1 Attention Control

Participants randomized to the attention control arm will be notified immediately, and will follow standard care as ordered by their individual, treating physician. Importantly, to reduce the potential for bias from greater attention and surveillance in the rehabilitation intervention group, participants in the attention control group will receive at least bi-weekly contact from study personnel during the first 3 months following the index hospitalization. This contact will be provided as a combination of telephone calls and specified study visits. Specifically, contact will be made with study visits at weeks 4 and 12 and with telephone calls at weeks 2, 6, 8, and 10. Further, in-person contact will be made within the first 2 weeks following discharge for the purposes of retention (section 8.2.2). Consistent with the rehabilitation intervention group, telephone contact will also be made at weeks 14, 16, 20, and 24. Information regarding symptoms, HF transitional management program use, medical compliance, activity level, rehabilitation received, medical resource utilization, and clinical events will be collected at each of these encounters.

Participants in the attention control arm will not receive any specific rehabilitation recommendations or exercise prescription from study personnel. They may, however, receive any physical or occupational therapy deemed appropriate by their usual clinical care providers, both during the hospitalization and as outpatients.

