7.4 Monitoring of Exercise and Rehabilitation

The details regarding the number of rehabilitation sessions attended as well as key markers of adherence to the exercise prescription and progression will be recorded and entered into the secure database by the study personnel supervising the rehabilitation and exercise training. In addition, participants in both the study intervention arm and the attention control arm will keep a diary of any exercise performed or any usual care rehabilitation received.

Participants in the rehabilitation intervention arm will be issued a pedometer to promote adherence to home exercise and activity goals.

Participant adherence with both exercise diary entries and wearing of a pedometer will be encouraged throughout the study during follow-up visits and phone calls.

8. Retention and Treatment Fidelity

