11.4 Short-term Cost Analysis

We will compare mean direct medical costs, indirect (patient time) costs, total costs and quality-adjusted survival over the six-month follow-up period in the REHAB-HF intervention patients versus attention control. We will generate utility weights from the EQ-5D-5L collected data.

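### Patient time, travel and out-of-pocket costs are counted only for the REHAB-HF programme, so the between-arm patient-time and total-cost differences in section 11.4 are gross programme costs, not incremental costs

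*Combined protocol and SAP*

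**What the plan says.** Section 11.3 defines the patient-time cost by the study programme: "To estimate time spent on REHAB-HF intervention, we will use information reported within the trial pertaining to adherence to protocol-required rehabilitation sessions". It adds patient-reported home exercise and values the hours at an average wage. On travel it says: "We will also ask patients to report the total amount of time they spend getting to each rehabilitation session". That sentence names no arm.

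Section 11.2 has the same scope. At 3 and 6 months, "patients will be asked to report information on direct non-medical costs incurred to comply with the REHAB-HF intervention". The items listed include transport, parking, gym fees and exercise equipment.

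Section 11.4 then sets the arms against each other: "We will compare mean direct medical costs, indirect (patient time) costs, total costs", over six months.

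Section 11.1 is wider. It collects all-cause medical resource use for each patient without restriction by arm, takes a societal perspective for direct medical costs, and states: "Professional services and costs for skilled nursing, home nursing and outpatient visits will be valued using Medicare fee schedules".

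Rehabilitation outside the programme is allowed. Under section 7.1, controls may "receive any physical or occupational therapy deemed appropriate by their usual clinical care providers", and their study contacts record the rehabilitation they received. Section 7.2.12 gives all participants the standard care their physician orders. Under section 7.4, participants in both arms "will keep a diary of any exercise performed or any usual care rehabilitation received".

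**The concern.** An incremental cost is the cost in one arm minus the cost in the other, with the same items counted in both. For patient time and out-of-pocket costs, sections 11.2 and 11.3 count only what is tied to the programme. A control participant who attends physical therapy, walks daily or buys equipment gives up time and money of the same kind, and none of it is in scope. An intervention participant who has usual-care therapy as well is also undercounted.

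The results exposed are the patient-time and total-cost differences in section 11.4, and the long-term cost-effectiveness analysis in section 11.5 if those costs are carried forward. No primary, secondary or safety result is involved.

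**Working it through.** **Scope, item by item, as the text stands**

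| Item | Intervention arm | Control arm |
|---|---|---|
| Medical cost of usual-care therapy | plausibly counted (11.1) | plausibly counted (11.1) |
| Programme sessions: time, travel, expenses | counted (11.2, 11.3) | none occur |
| Usual-care therapy: time, travel, expenses | not in stated scope | not in stated scope |
| Home or own exercise: time | counted (11.3) | not in stated scope |
| Exercise purchases and fees | counted (11.2) | not in stated scope |

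The third row is missing from both arms. The last two are missing from one arm only. The two kinds of omission therefore behave differently.

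**Is there a figure to reproduce?** No. The documents give no cost estimate, no cost variability and no rate of usual-care rehabilitation. What follows is in hours and rests on stated assumptions.

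**Counted supervised time.** Sections 7.2.1 and 7.2.4 give 3 outpatient sessions a week for 12 weeks, at about 60 minutes (range 45 to 75).
- Sessions: 3 × 12 = 36.
- Hours: 36 × 1 = 36 (27 at 45 minutes, 45 at 75 minutes).
- Travel and inpatient sessions are left out of this illustration.

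**Therapy component.** Let p_C and p_I be the shares of controls and of intervention participants who have usual-care therapy, and s the number of one-hour sessions each has. Then:
- error in the difference = (p_C − p_I) × s hours
- true difference = 36 − error.

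Assumed ranges: p from 0 to 50% in either arm, s from 12 to 36.

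| p_C | p_I | s | Error (h) | True difference (h) | Plan's 36 h against the truth |
|---|---|---|---|---|---|
| 25% | 0 | 12 | +3 | 33 | overstated by 3/33 = 9% |
| 50% | 0 | 36 | +18 | 18 | overstated by 18/18 = 100% |
| 25% | 25% | any | 0 | 36 | correct |
| 0 | 25% | 12 | −3 | 39 | understated by 3/39 = 8% |
| 0 | 50% | 36 | −18 | 54 | understated by 18/54 = 33% |

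The sign depends on which arm uses more usual-care therapy.

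**Exercise component.** Section 7.2.9 asks intervention participants to walk on days without a session, building up to 30 minutes.
- At goal from the start: 4 days × 0.5 h × 12 weeks = 24 h. This is an upper figure for walking, since the goal is reached gradually.
- The plan counts these hours against 0 h for controls.
- Assumption: controls walk a quarter to a half as much. Then 24 × 0.25 = 6 h to 24 × 0.5 = 12 h are omitted.
- With usual-care therapy equal in the two arms, the counted difference is 36 + 24 = 60 h. The true difference is 60 − 6 = 54 h to 60 − 12 = 48 h, an overstatement of 6/54 = 11% to 12/48 = 25%.

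Control exercise cannot be negative, so this component does not cancel when therapy use is balanced.

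**The case against.** The strongest reply is that section 11.1 already captures usual-care rehabilitation. A reader of 11.2 and 11.3 alone might infer that control-arm rehabilitation is costed at zero. The documents do not support that. Therapy delivered as outpatient visits or home care is all-cause resource use and carries a medical cost in either arm. Therapy visits are not named, so this should be confirmed, but at most the time, travel and out-of-pocket parts are missing. This objection stands.

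A second reply is that the wording leaves out usual-care therapy in both arms, so a reader who infers a bias of fixed direction goes too far. That stands for therapy: the error is zero if use is equal and reverses if the intervention arm uses more. It does not answer the exercise component, where one arm's hours and purchases are counted and the other's are not.

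A third reply is that the text is not fully closed. The travel question names no arm, and both arms keep diaries. This shows that some of the data will exist. It does not say that they will be valued, and the stated purpose in both sections is the programme.

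Lastly, a reader might infer that the gap could turn a cost-saving result into a cost-adding one for the economic objective or the payment models. The first objective in section 2.3 compares medical costs including the cost of rehabilitation therapy, and the offset analysis in section 11.6 sets programme cost against savings in medical resources. Neither names patient time or personal expenses.

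**Conclusion.** The point holds in a limited form. The patient-time and total-cost differences in section 11.4, and section 11.5 if they are carried forward, would be gross programme costs and not incremental costs. The exercise component tends to overstate the intervention's incremental cost. The therapy component can err either way.

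The size cannot be computed from the documents. The hours shown rest on assumed shares, session counts and control walking, and hours do not translate into a share of total cost without cost figures. A reader might set 6 to 12 control therapy visits against 36 sessions and infer an overstatement of 20% to 50% (36/30 − 1 and 36/24 − 1). Those visits are assumed, the calculation takes the intervention arm to have no usual-care therapy, and it leaves out home-exercise time, so it should not be quoted as the effect.

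The medical-cost objective and the payer offset analysis are not directly affected. This is a worthwhile correction of minor severity.

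**What to change.** - Reword sections 11.2 and 11.3 so that time, travel and out-of-pocket costs are collected and valued for all rehabilitation and exercise in both arms. Draw on the diaries of section 7.4 and the contacts that record rehabilitation received. Ask the same questions of both arms at 3 and 6 months and apply the same hourly wage.
- In section 11.1, confirm that physical and occupational therapy visits count as resource use.
- In section 11.4, say whether direct non-medical costs enter total costs; they are not named there.
- Report the programme-only cost separately as a sensitivity analysis.

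The cost is a few extra questions for control participants at visits or calls already scheduled, and some data entry from diaries already kept. The questions should be in place prospectively, because travel and expenses that were never asked about may not be recoverable later.
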